This is a pragmatic trial that will study outcomes of routine care. Thus, rather than recruiting participants, the intervention and control arms will be compared using data available in routine TB laboratory and treatment registers for consecutive patients who present to participating health centers during the two-year trial period and meet eligibility criteria (estimated N=11,283 patients).

Participants for mixed methods and health economic sub-studies

Patient Cost and Satisfaction Surveys: The patient cost and satisfaction surveys will be administered during the baseline (pre-randomization) period (N=20/site; 400 total) and in the second year after randomization (N=40/site, 800 total). Health center staff will assist with identification and recruitment of patients who are interested in participating in the surveys (from among patients providing sputum samples or receiving results). Participation will be voluntary. Research staff will then contact interested patients by phone at the end of their health center visit to review the verbal consent script, answer questions the patient may have, and administer the survey to consenting patients.

Provider Survey: The provider survey will be administered during the baseline (pre-randomization) period and in the second year after randomization. All eligible providers at each study site (N=5-10/site; 100-200 total) will be invited to participate in the survey. Participation will be voluntary and written informed consent will be obtained.

Provider Focus Group Discussions and Interviews: Focus group discussions will occur during the second year after randomization and semi-structured interviews after the trial is completed. All eligible providers at intervention sites (N=5-10/site; 50-100 total) will be invited to participate in focus group discussions. Providers (N=20-30) at low- and high-performing sites will be invited to participate in semi-structured interviews. Participation in focus group discussions and interviews will be voluntary and written informed consent will be obtained.

[figure not shown]
Intervention and Control (Wait-list) Arms

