Patient demographic and clinical (HIV and TB testing and treatment) data will be collected at all sites. At the first pre-trial site visit, project staff will photograph each page of the following data sources from January 2016 until the visit date: 1) NTLP Presumptive TB, Laboratory and Treatment registers and 2) Xpert laboratory requisition forms. Project staff will also train two health center staff (one primary, one backup) identified by the health center in-charge to take photos of these data sources every two weeks for the duration of the project (between October 1, 2018 and March 31, 2020) using a camera-enabled smartphone, and to upload the photos to a central secure server through REDCap mobile. Health center staff will be trained to delete photos from the phone after upload confirmation. In addition to these data sources, study staff will 1) Review pre-ART and ART registers during scheduled site visits to verify ART status for any HIV-positive patient missing ART information; 2) review additional data sources (e.g., clinic registration logbook) as needed at scheduled site visits to attempt to track down key information missing from primary data sources; and 3) call MDR TB treatment centers to determine referral, additional testing and treatment status and outcomes for patients with RIF resistance identified through Xpert testing.

Symptom Screening

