A questionnaire adapted from the routine TB case finding guide will be administered to document TB symptoms reported at each patient’s initial visit to the health clinic. This information will be used to assess the proportion of patients referred for TB testing who were eligible for testing based on reported symptoms. Surveys will be administered by phone two weeks after the patient’s initial clinic visit to avoid influencing the primary outcome. Surveys will also be administered in-person to patients who provide a sputum sample for TB testing. In-person surveys will take place during quarterly site visits. All patients who are at least 18 years old, meet the main study inclusion criteria, and enrolled over a specified three-month period will be eligible for participation in the symptom screening activity. Due to logistical feasibility, however, it is anticipated that only patients with a documented valid phone number and patients selected for in-person interviews during quarterly site visits will be included in this activity. Study staff will prioritize clinics with a smaller proportion of patients with phone numbers available for in-person interviews.

Patient surveys

We will administer cost and satisfaction with care surveys to 20 patients at each health center (N=400 total) in the pre-randomization period and to 40 patients at each health center (N=800) at least 6 months post-randomization (April-September 2019). The two surveys will involve the same patients when feasible, but administered to different patients if a patient does not wish to complete both.

The cost survey will collect data on direct and indirect costs (time to complete visit, lost wages, etc.) of TB diagnostic evaluation. Cost data collection will be based on the Tool to Estimate Patient Costs developed by the TB Coalition for Technical Assistance, which we have already adapted and used in Uganda.

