c) Health facility environment	c) Sum of score on 2 question items (Q4 and 5)
d) Provider interpersonal skills	d) Sum of score on 5 question items (Q7-11)
e) Provider technical competence	e) Sum of score on 4 question items (Q12-15)
Provider survey:	
a) Intention	a) Score on 1 question item (Q4)
b) Attitudes/beliefs	b) Sum of score on 3 question items (Q5a, 6a, and 6b)
c) Social norms/expectations	c) Sum of score on 2 question items (Q5b, 6c and 6d)
d) Self-efficacy/behavioral control	d) Sum of score on 5 question items (Q5c, 6e and 6f)

Intervention arm only		
Outcome	Numerator	Denominator
Process metrics:		
a) GeneXpert device non-operation days	a) GeneXpert device non-operation days ¹	a) Total number of lab operation days ¹
b) Proportion tested by GeneXpert:	b) Number with GeneXpert result date	b) Number tested by GeneXpert ²
1. On same day as initial sputum submission	1. Same as initial sputum submission date ²	
2. By next day after initial sputum submission	2. By next day after initial sputum submission date ²	
c) Proportion with indeterminate results	c) Number with coded error, invalid or no test result ²	c) Number of initial GeneXpert tests done ²
d) Proportion with coded error result	d) Number with coded error result ²	d) Number of initial GeneXpert tests done ²
e) Proportion with invalid result	e) Number with invalid result ²	e) Number of initial GeneXpert tests done ²
f) Proportion with “no test” result	f) Number with “no test” result ²	f) Number of initial GeneXpert tests done ²
g) Proportion with GeneXpert test repeated if initial result indeterminate	g) Number with second GeneXpert result ²	g) Number with initial indeterminate GeneXpert result ²
	h) # treated on same day as initial health center visit ³	h) # Xpert-positive ²

h) Proportion treated on same-day if Xpert-positive	i) Number of Report Cards with Comments section filled ⁴	i) Total number of report cards issued to health centers ³
i) Proportion of report cards reviewed at staff meetings	Variation in and barriers to intervention strategy uptake	Themes emerging from focus group discussions, semi-structured interviews with health center staff

Source of data: ¹ Health center laboratory log; ² GeneXpert Software; ³ Treatment register; ⁴ Performance feedback report card

IV. Cost-effectiveness/Modeling Outcomes

Outcome	Definition	Source

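### Unblinded health center staff help find the cost and satisfaction survey respondents, and no selection rule limits their discretion, so the between-arm survey comparison is open to selection that shifts after randomization

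*Combined protocol and SAP*

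**What the plan says.** The current protocol (section on participants for the mixed methods and health economic sub-studies) sets two survey waves: "during the baseline (pre-randomization) period (N=20/site; 400 total") and "in the second year after randomization (N=40/site, 800 total"). On recruitment it says: "Health center staff will assist with identification and recruitment of patients who are interested in participating in the surveys", drawn "from among patients providing sputum samples or receiving results". Then: "Research staff will then contact interested patients by phone at the end of their health center visit", to go through the verbal consent script and run the survey. Participation is voluntary. The Patient surveys section dates the second wave April to September 2019.

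No section adds a selection order, a quota by visit type, a log of patients approached or declining, or a comparison of respondents with register patients.

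The Implementation Outcomes table lists patient costs and satisfaction as comparisons across arms. Provider interpersonal skills is defined as "Sum of score on 5 question items (Q7-11"), and provider technical competence is the sum of four further items. Statistical Analysis, Aim 2, compares the change from baseline by arm at cluster level, allowing for the strata and for other baseline imbalances. The current SAP covers effectiveness outcomes only, so it adds nothing on the surveys.

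SAP section 3.6 calls the trial open-label. It also mentions coded clusters to blind staff, but clinic workers who run an onsite device and receive Report Cards cannot be blind to their own arm.

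**The concern.** The main trial leaves clinics no choice about who counts: it takes consecutive patients by complete enumeration (SAP section 4.3). The survey leaves that choice open. Workers who know their arm can influence which patients are put forward, and some of the scored items concern those workers or their close colleagues.

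Constant selection is not the difficulty. If a clinic favors contented patients equally in both waves, the change score removes it. The difficulty is selection that alters once the intervention has begun in one arm. Neither subtracting baseline nor adjusting for baseline imbalance can remove that, and nothing recorded would reveal it.

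Cost has a separate and more mechanical route. The section on the intervention and control arms describes up to 4 visits in the control arm, against an aim of diagnosis and treatment at the first visit in the intervention arm. A convenience sample of patients giving sputum or collecting results can therefore catch different points of the pathway in each arm, with different costs accrued.

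At stake are the between-arm satisfaction and cost results and the patient-cost inputs to Aim 3.

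**Working it through.** **1. The plan's own survey totals.** 20 per site × 20 sites = 400, and 40 × 20 = 800. Both reproduce. The protocol bases these numbers on feasibility and gives no SD, intracluster correlation, effect size or power for the surveys.

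**2. Room to choose.** The follow-up window is 6 of the 18 enrolment months. Even accrual is assumed.
- SAP section 3.5 estimate: 5,360 / 20 = 268 per site; × 6/18 = 89; 40/89 = 45%.
- Current protocol estimate: 11,283 / 20 = 564 per site; × 6/18 = 188; 40/188 = 21%.

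So 55% to 79% of attendees would not be surveyed. (The protocol also places this wave in the second year after randomization. April to September 2019 is within a year of the 22 October 2018 start. The two statements need reconciling; the dated window is used here.)

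**3. Precision of the planned comparison, in SD units.** Assume a total variance of 1 with 0.95 within clinics. The remaining 0.05 may be a lasting clinic effect, which drops out of the change, or clinic-by-period variation (τ), which does not.

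Variance of one clinic's change = 0.95 × (1/20 + 1/40) + 2τ = 0.07125 + 2τ.

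SE of the arm difference with 10 clinics per arm = √(2 × variance / 10).
- τ = 0: variance 0.07125, SE = √0.01425 = 0.119.
- τ = 0.025: variance 0.12125, SE = 0.156.
- τ = 0.05: variance 0.17125, SE = √0.03425 = 0.185.

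**4. Chance of p<0.05 with no true effect.** Suppose selection moves one arm's follow-up mean by b. The test is two-sided at 5% on 16 degrees of freedom (20 clinics less 4 stratum-by-arm cells), critical value 2.12, with noncentrality b/SE.

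| Assumed shift b | τ = 0 | τ = 0.025 | τ = 0.05 |
|---|---|---|---|
| 0.1 SD | 12% | 9% | 8% |
| 0.25 SD | 50% | 33% | 25% |
| 0.4 SD | 88% | 68% | 53% |

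The τ = 0 column is the upper edge of this range. Neither b nor τ comes from the documents.

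**5. What the planned adjustment covers.** Strata and baseline imbalance are both fixed before the intervention starts. A selection shift that arises afterwards is outside both.

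**The case against.** The strongest reply is that the wording is modest. Staff assist; they do not decide alone. Patients must be interested and must consent, and research staff hold the interview by phone, which limits pressure on the answers. Many respondents are only providing sputum, when staff have little basis for guessing how satisfied they will be. This stands, and it rules out saying that providers choose their own raters. It does not supply a rule for who is asked.

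A reader might also infer that the monthly Report Cards give intervention clinics a reason to recruit satisfied patients. The documents do not support that. Under Performance Feedback, the cards show TB diagnostic evaluation quality indicators; neither satisfaction nor patient cost is listed, and no section says that survey results return to clinics. The route to bias is open, but no one-sided incentive is documented.

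A third reply concerns the remedy of sampling from records and phoning later, as in Symptom Screening ("Surveys will be administered by phone two weeks after" the first visit). That would lengthen recall for costs now collected at the end of the visit. It would also depend on recorded phone numbers, whose availability that section treats as uneven across clinics. This stands, and the fix below avoids it.

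Finally, these are Aim 2 implementation outcomes sized on feasibility. That is true and limits the weight of the point.

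**Conclusion.** The concern holds in a limited form. Unblinded clinic staff have unregulated influence over who enters the survey sample, respondents rate providers at the same clinic, and the planned change-from-baseline analysis cannot remove selection that shifts in one arm after randomization. For cost, unbalanced visit mix is the clearer mechanism.

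The documents show an open route to bias, not that bias occurred, nor its size or direction. The illustrative false-positive rates of 8-12%, 25-50% and 53-88% rest on assumed shifts of 0.1, 0.25 and 0.4 SD and an assumed clinic-by-period variance between 0.05 and 0. They should be read as a range and not as a prediction.

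A reader might infer that the main result is at risk. It is not: the primary outcome is built from routine records of consecutive patients and does not use the survey. The point is confined to the satisfaction and cost comparisons and the patient-cost inputs to Aim 3. It is a cheap improvement.

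**What to change.** Replace staff-assisted identification with one fixed rule in both arms:

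- On dates set by research staff, offer the survey to every consecutive eligible patient providing sputum or receiving results, until the site quota is met.
- Keep the call by research staff at the end of the visit, so that cost recall does not lengthen.
- Have research staff check the list of patients offered the survey against the register photos. Clinics already "take photos of these data sources every two weeks for the duration of the project".
- Record visit type for each respondent.
- Report by arm the numbers offered, declining and unreachable, and compare respondents with register patients.
- The baseline wave used staff-assisted recruitment. If only the follow-up wave changes, also report the post-randomization between-arm comparison on its own, because the change score would then mix two sampling methods.

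The survey sizes of 400 and 800 stay as they are. The cost is protocol wording and slightly more coordination on survey days. Refusal and non-contact will remain, but they become visible by arm.

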name, sex, age, and exam type from the Laboratory Register. Once patients have been matched across all data sources, the staff will run a series of reports in REDCap to verify the completeness and accuracy of key variables impacting patient eligibility and/or study outcomes: age, sex, HIV status, examination type, smear and Xpert test results, outcomes dates (sputum collection, test results, start and end of treatment, treatment outcome), and treatment status. Study staff will review the original data photographs to verify the information is missing, and they will compile a list of follow up items for each health center. Research staff will phone health center staff after each 2-week period of data is extracted to resolve missing information and clarify any discrepancies or uncertainties in matching. Once the health center reviews the missing and/or inaccurate data, the study staff will update REDCap. The UCSF study coordinator will visit Uganda 2-3 times a year and review a random sample of forms and primary data sources for quality assurance.

Statistical Analysis

Aim 1

A detailed Statistical Analysis Plan will be developed. Briefly, we will calculate and compare all effectiveness outcomes for the two trial arms using an intention-to-treat analysis. We will use descriptive statistics and 95% confidence intervals to summarize the yield, efficiency, and speed outcomes for the two arms by site. To assess the intervention effect on outcomes, we will use methods appropriate for randomization of a small number of clusters and accounting for the stratified design.²⁶ A cluster-level analysis, giving each cluster equal weight, will be conducted to calculate unadjusted ratio and difference effect measures, and their associated 95% confidence intervals. Adjusted effect estimates will also be calculated taking into account any imbalance of important factors at baseline by study arm. Pre-specified subgroup analyses (e.g., gender and HIV status) will be conducted for the primary outcome. A detailed statistical analysis plan will document methods used for the analysis of primary and secondary outcomes, and document pre-specified sub-group analyses.

Aim 2

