- **Number treated:** Number of eligible patients entered into the NTLP Treatment register as having started Category I or II regimen.
- **Number completing treatment:** Number treated and with a treatment outcome of cured or completed entered into the NTLP Treatment register.
- **Number died, among those initiated on TB treatment:** Number treated and with a treatment outcome of died entered into the NTLP Treatment register within six months of enrolment , or number treated and confirmed dead by next of kin with a date of death within six months of enrolment.
- **Number died, among those with confirmed TB:** Number diagnosed and with a treatment outcome of died entered into the NTLP Treatment Register within six months of enrolment, or number diagnosed and confirmed dead by next of kin with a date of death within six months of enrolment.
- **Number died, among all those eligible:** Number treated and with a treatment outcome of died entered into the NTLP Treatment register within six months of enrolment, or number traced with a death recorded
- **Time-to-diagnosis:** Number of days from *date enrolled* to earliest date of positive smear or valid Xpert result recorded in NTLP Presumptive TB register, NTLP Laboratory register, GeneXpert laboratory requisition form, or NTLP treatment register within six months of enrolment . For the control arm, attempts will be made to abstract the missing Xpert result dates from machine data from GeneXpert machines at testing hubs. For patients with microbiologically confirmed TB who are missing the smear or Xpert result date, the date of treatment initiation will be used as the date of diagnosis.
- **Time-to-treatment:** Number of days from *date enrolled* to treatment start date entered into NTLP Treatment register if treatment start date is within six months of enrolment.

Primary Outcome

Outcome	Numerator	Denominator
Number treated for microbiologically-confirmed TB within 14 days of date enrolled.	Number diagnosed and time-to-treatment within 14 days	None

Secondary Outcomes

A. Testing		
Outcome	Numerator	Denominator
Number referred for TB testing	Number referred for testing	None
Proportion completing testing	Number completing testing	Number enrolled
B. Diagnosis		
Outcome	Numerator	Denominator
Number diagnosed with microbiologically-confirmed TB*	Number diagnosed	None
Proportion diagnosed with microbiologically-confirmed TB*	Number diagnosed	Number enrolled

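### No rule keeps the fortnightly treatment-status queries to clinics outside the 14-day primary window, which could pull the treated-count ratio towards 1 by an unknown amount

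*Combined protocol and SAP*

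**What the plan says.** The amended protocol (Patient-level data collection) states: "Patient demographic and clinical (HIV and TB testing and treatment) data will be collected at all sites". Two trained staff at each clinic "take photos of these data sources every two weeks for the duration of the project".

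Under Data Management, study staff match each patient across the registers, ending with the Treatment Register. They then run completeness reports on variables that include "outcomes dates (sputum collection, test results, start and end of treatment, treatment outcome), and treatment status". Unresolved items go on a list for each clinic, and "Research staff will phone health center staff after each 2-week period of data is extracted to resolve missing information". The same calls settle discrepancies and doubtful matches. No interval between extraction and call is given, and no minimum time since a patient's enrolment.

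The primary outcome (current SAP, section 3.4) is "Number diagnosed and time-to-treatment within 14 days", counted from date enrolled to the start date in the Treatment Register.

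The protocol guards against this kind of influence in one other place. Under Symptom Screening, the phone survey waits until two weeks after the "initial clinic visit to avoid influencing the primary outcome". That section also says: "Surveys will also be administered in-person to patients who provide a sputum sample for TB testing". These in-person surveys take place at quarterly visits, and the activity covers one three-month enrolment period.

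**The concern.** A patient with a positive result and no treatment entry is a natural item for the follow-up list. The most recent batch holds patients enrolled 0 to 14 days before it closed. With any delay under 14 days, a call can therefore name someone whose primary outcome is still open, and asking a clinic whether that patient has started treatment can work as a reminder.

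The reminder belongs to neither arm's care. The control arm is expected to lose a larger share of its confirmed patients before treatment, so it has more room to gain. Treatment prompted by the study would then be counted as routine control performance. The estimated ratio would shrink, and the same effectiveness data feed the cost-effectiveness model in Aim 3. Without a record of query dates, nobody could tell afterwards whether this had happened.

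**Working it through.** **1. The plan's own figures.** SAP section 3.5, Table 3, gives detectable geometric mean ratios (GMR) for the count outcome. Use GMR = exp[(z0.975 + z_power) × SD × √(2/n)], with two-sided 5% (sidedness is not stated) and n = 9 per arm, which is 10 less the one extra cluster added for stratification.

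- SD 0.2: exp(2.802 × 0.2 × 0.4714) = 1.302 at 80% power; exp(3.242 × 0.2 × 0.4714) = 1.357 at 90%.
- SD 0.3: 1.486 and 1.582.

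These match the stated 1.30, 1.36, 1.49 and 1.58. The SAP's cascade example (1000 people, 10% prevalence) also reproduces: 95 × 0.93 = 88.35 and 40 × 0.70 = 28.

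**2. Can a call fall inside the window?** Assume even enrolment over a 14-day batch and a call L days after the batch closes. L is not stated. The share of the batch still before day 14 is (14 − L)/14, or zero if negative:

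| L (days) | 0 | 3 | 7 | 10 | 14 or more |
|---|---|---|---|---|---|
| Share | 100% | 79% | 50% | 29% | 0% |

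To be queried as confirmed but untreated, a patient must already have a positive result in the photographed register. If the result takes D days from enrolment, the share becomes (14 − L − D)/14. SAP section 3.4 says that diagnosis in control could take 7-10 days, depending on sample transport to the Xpert hub.

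- D = 7: 50% at L = 0, 29% at L = 3, none from L = 7.
- D = 10: 29% at L = 0, 7% at L = 3, none from L = 4.

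A result that misses one batch is first seen at the next, when the patient is past day 14.

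**3. Effect on the treated-count ratio.** Let f be the share of confirmed, otherwise untreated patients who start treatment by day 14 because of a call, equal in both arms. With S confirmed and pre-treatment loss l, the number treated is S × [1 − l(1 − f)]. Inputs from SAP section 3.5:

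- original assumptions: S = 95 (intervention) and 40 (control), l = 7% and 30%;
- revised assumptions: sensitivity doubled (80 and 40), l = 15% (the upper limit of the stated range) and 30%.

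The values of f are assumed.

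| f | Original: treated I / C | Ratio (factor) | Revised: treated I / C | Ratio (factor) |
|---|---|---|---|---|
| 0 | 88.35 / 28.0 | 3.16 (1) | 68.0 / 28.0 | 2.43 (1) |
| 0.10 | 89.02 / 29.2 | 3.05 (0.966) | 69.2 / 29.2 | 2.37 (0.976) |
| 0.25 | 90.01 / 31.0 | 2.90 (0.920) | 71.0 / 31.0 | 2.29 (0.943) |

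**4. Direction when the arms respond differently.** The ratio is unchanged when f_I × l_I/(1 − l_I) = f_C × l_C/(1 − l_C). So it moves away from 1 only if f_I/f_C exceeds (0.30/0.70)/(0.07/0.93) = 5.7 on the original figures, or (0.30/0.70)/(0.15/0.85) = 2.4 on the revised ones.

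**5. Power.** Take the plan's 90% points (GMR 1.36 with SD 0.2; GMR 1.58 with SD 0.3), apply the factors above and keep the SD unchanged. Power is Φ{ln(GMR × factor)/[SD × √(2/9)] − 1.96}. For example, 1.36 × 0.966 = 1.314, and 0.273/0.0943 − 1.96 = 0.94, giving 83%. Across both points and both sets of loss figures, power is 83-87% at f = 0.10 and 66-81% at f = 0.25.

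**The case against.** Several points count against this concern.

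- **The calls are data cleaning, made to clinic staff in both arms.** The documents do not say that a confirmed patient missing from the Treatment Register is queried as untreated; the record might simply be coded as no treatment. This stands as a limit. That such a query is made is an inference, though a natural one, since treatment status is a checked item and the calls also cover doubtful matches.
- **The delay is unlikely to be near zero.** Photographs must be compiled, four sources matched, reports run and images rechecked first. This stands: at 14 days or more the problem disappears.
- **Control patients diagnosed through the hub would often not be visible in time.** This largely stands and weakens the direction as well as the size. If every untreated control patient had D = 10 and every intervention patient D = 0, reach at L = 0 would differ by 100/29 = 3.5, which is above the 2.4 threshold but below 5.7. Against that, the SAP's 40% control yield is the sensitivity of smear microscopy, and smear-positive patients appear in the register early.
- **Clinics may be unable to act.** Table 2 of the protocol lists weak patient tracking and failure to return among the barriers. This stands: no response rate can be taken from the documents.
- **Attenuation is conservative for a superiority test.** True of the test, but not of the effect estimate or of the cost-effectiveness model that uses it.

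**Conclusion.** The gap is real: queries on the variable that defines the primary outcome have no timing rule, while a survey about symptoms has one. Any resulting bias is a possibility, not a demonstrated fact. It would probably be towards 1, and its size is unknown and could be zero. For illustration, rescue of 10% of untreated confirmed patients in both arms multiplies the ratio by 0.97-0.98, and rescue of 25% by 0.92-0.94. These figures rest on the SAP's loss assumptions, an equal response in both arms and assumed values of f.

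Three stronger readings are tempting, and the documents do not support them.

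- **A reader might infer that the calls reach more control patients.** That holds as a share of confirmed patients. In numbers per 1000 evaluated it holds on the original figures (40 × 0.30 = 12 against 95 × 0.07 = 6.65), but at the revised limit the counts are equal (12 against 80 × 0.15 = 12).
- **A reader might quote the fall in the linkage ratio.** With L = 7 and half of the reachable patients responding (f = 0.25), it goes from 93/70 = 1.33 to 94.75/77.5 = 1.22. That is linkage among confirmed patients, not the primary count. The multiplier is the same 0.92, but linkage loses about a third of its excess over 1, whereas the count ratio loses about 12% (3.16 to 2.90), or about 10% on the revised figures (2.43 to 2.29).
- **A reader might conclude that control no longer represents standard care.** Nothing in the documents shows that the calls changed treatment.

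The point merits a change because the remedy is small, not because the trial's conclusion is shown to be at risk.

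**What to change.** In Data Management, release a query on treatment status or treatment start date only when the record is at least 15 days past date enrolled. All other queries run as planned. Date-stamp every treatment query and tabulate these by arm.

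In SAP section 4.4.3, add one sensitivity analysis of the primary count. Patients who started treatment after a treatment-status query made inside the window are not counted as events. Describe it as a bound, because some of them would have been treated anyway. If the timing rule is followed throughout, this analysis changes nothing; it covers queries made before the rule takes effect or released early.

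For the in-person symptom surveys, flag the patients only. Removing them as events would delete genuine same-day treatments.

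If the sponsor prefers not to delay any query, the date stamp and the bounding analysis alone would show how large the effect could be.

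The cost is one filter in the REDCap query report, one date field and one extra model. The downside is that treatment queries are resolved up to about two weeks later.
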